### 6.4.1.2 Graphical Summary of Data from Primary Efficacy Endpoint

Mean number of micturitions per 24 hours at each visit and change from baseline in mean number of micturitions per 24 hours will be plotted for FAS: mean (SEM) values will be presented for each visit.

LS Mean change from baseline in mean number of micturitions per 24 hours at each visit and change from baseline in mean number of micturitions per 24 hours will be plotted for FAS: mean (95% CI) values will be presented for each visit.

### 6.4.1.3 Subgroup Analysis for Primary Efficacy Endpoint

For the primary efficacy endpoint, descriptive statistics (n, mean, SD, minimum, median, maximum) and the statistical comparison within each group will be calculated for mean change from baseline at each visit using the same MMRM model described in Section 6.4.1.1 for the following subgroup: Prior OAB treatment (Yes vs. No).

Appendix 9.2 reports a non-exhaustive list of prior OAB treatment (not allowable during the study period).

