For this study, the treatment estimand is considered appropriate because of the fact that the response of subjects prior to switching is of primary interest. i.e., the estimate for 50 mg of mirabegron should be estimated from subjects who were randomized to 50 mg and the estimate for 25 mg should be estimated from subjects who were randomized to 25 mg while they were treated with 25 mg.

Study Population:

Male and female adult Chinese subjects (\geq 18 years of age) with overactive bladder (OAB; as defined according to the International Continence Society [ICS]).

Number of Subjects:

A total of 249 male and female Chinese subjects with OAB will be randomized into 2:1 ratio within 2 dose groups (50 mg of mirabegron and 25 mg of mirabegron).

Study Design Overview:

[figure not shown]
The study follows an open-label, randomized, 12-week, prospective, interventional postauthorization design for the treatment of OAB in approximately 249 Chinese subjects. Each subject will participate in one 12-week treatment period.

This study is designed to support the Imported Drug License (IDL) renewal and mirabegron safety surveillance in China. The data-cut with summaries and the planned primary analysis for the end of this study will be used for IDL renewal. Subjects fulfilling the screening inclusion/exclusion criteria will be randomized in 2:1 ratio to 50 mg mirabegron and 25 mg mirabegron using a computer-generated randomization to reduce selection bias. Treatments will be administered once daily orally recommended at the same time after meal during a 12-week, open-label treatment period. Study visits will take place at weeks 4, 8 and 12. For 25 mg mirabegron group, a dose escalation to 50 mg is permitted on visit 3 and visit 4 according to investigators' discretion.

Treatment Groups and Duration:					
Arm/IP Name	Mirabegron (BETMIGA®) Test product				
Use					
Dose	25 and 50 mg				
Frequency/Duration	Once daily doses for 12 weeks				
Route	Oral				
IP: investigational product					
The anticipated duration of the study for each subject, including screening and follow up, is approximately 16 weeks.					

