9.4.2.2.1 Subgroup Analysis

The same analysis (MMRM) as for the primary endpoint will be applied to change from baseline for the following subgroups:

• Prior OAB treatment

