# **3** SAMPLE SIZE

The sample size for this study is based upon change from baseline for mean number of micturitions/24 hours within a single treatment arm. Change from baseline will be tested to determine if the change is different from zero i.e., a change in mean number of micturitions/24 hours. When the sample size is 125, a single group t-test with a 5% two-sided significance level will have 80% power to detect a change of 0.9 micturitions with a SD of 3.562 [Neurourology and Urodynamics, 2015]. Assuming 25% of the subjects will drop out, about 166 subjects will be enrolled to yield 125 evaluable subjects in 50 mg group.

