### 6.4.1.1 Primary Analysis for Primary Efficacy Endpoint

The primary estimator for the primary estimand as defined in [Section 2.1.1 Estimand] will be calculated according to the evaluation of the primary efficacy endpoint. The primary efficacy endpoint will be analyzed using a Mixed Models Repeated Measures (MMRM). The MMRM model will include visit (the repeated term), treatment group (25 mg [total] or 50 mg [as-randomized]), pooled site, sex and the interaction between treatment group and visit as fixed effects and baseline measurement (the mean number of micturitions per 24 hours) as covariate. The algorithm to pool sites will be generated and documented prior to data base lock (Appendix 9.1). If the inclusion of pooled sites creates modeling problems, then dropping that factor will be considered. Subject will be identified as subject in the repeated statement.

The hypothesis for comparisons is given as follows:

- H0: The adjusted mean change from baseline at week 12 in mean number of micturitions per 24 hours in the 50 mg group is not different from zero.
- H1: The adjusted mean change from baseline at week 12 in mean number of micturitions per 24 hours in the 50 mg group is not equal zero.

Statistical testing will be done 2-sided at a 5% significance level.

The MMRM model results will be presented by treatment least squares (LS) means ( $\pm$  standard error [SE]) along with 2-sided 95% confidence intervals (CIs) and associated p-value for mean changes from baseline at weeks 4, 8 and 12 (the primary endpoint). Data from subjects who switch from 25 to 50 mg mirabegron will not be included in MMRM model. Data from those subjects prior to switching will still be included in the MMRM model with treatment equal to 25 mg.

Model fitting will be visually assessed. A scatter plot of residuals versus predicted values, along with histogram and normal probability plots will be produced.

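### The only planned subgroup, prior OAB treatment, is analysed by within-group tests against zero, and no Yes-versus-No contrast is planned

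*SAP*

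**What the plan says.** Protocol 9.4.2.2.1 lists prior OAB treatment as the only subgroup factor and states: "The same analysis (MMRM) as for the primary endpoint will be applied to change from baseline for the following subgroups". SAP 6.4.1.3 keeps that single factor (Yes vs. No), adds descriptive statistics, and says that "the statistical comparison within each group will be calculated for mean change from baseline at each visit using the same MMRM model" set out in SAP 6.4.1.1.

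The SAP 6.4.1.1 model contains visit, treatment group, pooled site, sex, treatment-by-visit and baseline. It has no term for prior OAB treatment. Its null hypothesis is that the adjusted mean change at Week 12 "in the 50 mg group is not different from zero", and "Statistical testing will be done 2-sided at a 5% significance level". Its outputs are LS means, SEs, 95% CIs and p-values by treatment at Weeks 4, 8 and 12.

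Neither document plans a prior-treatment term, an interaction, or a Yes-minus-No difference with a CI. Neither gives the expected size of the two subgroups; SAP 6.2.3 only tabulates prior treatment at baseline.

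**The concern.** A subgroup analysis is read for one purpose: to see whether the result differs between the subgroups. Two tests, each asking whether its own subgroup changed from zero, do not address that. One significant and one non-significant p-value is compatible with identical true changes, and the pattern is common when each subgroup has modest power.

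On a literal reading the plan produces up to 2 subgroups × 2 arms × 3 visits = 12 subgroup p-values, none of which compares Yes with No. SAP 2.2 says the study supports the import licence renewal. If one subgroup is significant and the other is not, the report could be taken to show that mirabegron works only in previously treated or only in untreated patients, with no planned estimate to check that against.

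**Working it through.** **Inputs from the documents.** SAP 3 gives the design: "When the sample size is 125, a single group t-test with a 5% two-sided significance level will have 80% power" and "to detect a change of 0.9 micturitions with a SD of 3.562". For enrolment: "Assuming 25% of the subjects will drop out, about 166 subjects will be enrolled to yield 125 evaluable subjects in 50 mg group". The two-sided 5% level also applies to the MMRM test (SAP 6.4.1.1).

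**Assumptions.** The Yes/No split is not in the documents, so 50:50, 70:30 and 80:20 are shown. A one-sample t-test stands in for the Week 12 LS mean on 50 mg. Both subgroups have the same true change and the same SD.

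**Step 1: reproduce the plan's figure.** The noncentrality is (0.9/3.562) × √n. At n = 125 it is 0.2527 × 11.18 = 2.82, and the noncentral t gives power 0.800. The smallest n reaching 80% is 125, so the plan's figure is reproduced. Enrolment: 125/0.75 = 166.7, against about 166 in the plan; 166 × 1.5 = 249.

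**Step 2: one significant, one not.** With independent subgroups of power p1 and p2, P(exactly one significant) = p1(1 − p2) + p2(1 − p1).

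| Split of 125 | p1 | p2 | P(exactly one significant) |
|---|---|---|---|
| 62/63 (50:50) | 0.499 | 0.506 | 0.499×0.494 + 0.506×0.501 = 0.50 |
| 88/37 (70:30) | 0.650 | 0.322 | 0.650×0.678 + 0.322×0.350 = 0.55 |
| 100/25 (80:20) | 0.706 | 0.228 | 0.706×0.772 + 0.228×0.294 = 0.61 |

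Simulation (40,000 runs) gives 49.7%, 55.6% and 61.3%. If all 166 were analysed, the figures would be 47%, 54% and 64%.

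**Step 3: dependence on the true change and SD** (125 evaluable).

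| Common change | SD | 50:50 | 70:30 | 80:20 |
|---|---|---|---|---|
| 0.5 | 3.562 | 31% | 32% | 33% |
| 0.9 | 3.562 | 50% | 55% | 61% |
| 1.2 | 3.562 | 38% | 49% | 61% |
| 1.5 | 3.562 | 17% | 31% | 48% |
| 1.8 | 3.562 | 5% | 15% | 32% |
| 2.5 | 3.562 | 0% | 1% | 8% |
| 0.9 | 2.5 | 32% | 44% | 58% |

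**Step 4: the direct contrast.** When the true changes are equal, a 5% test of Yes minus No shows a false difference in 5% of trials, whatever the split or effect. Its precision is SE = 3.562 × √(1/n1 + 1/n2), with 95% half-width 1.96 × SE:

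- 62/63: SE 0.637, half-width 1.25
- 88/37: SE 0.698, half-width 1.37
- 100/25: SE 0.796, half-width 1.56

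The difference detectable with 80% power is 1.79, 1.96 and 2.23. Power for a true difference of 0.9 is 29%, 25% and 20%.

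**The case against.** The strongest reply is that this is one non-confirmatory subgroup. No objective concerns prior treatment, the only stated hypothesis is the overall 50 mg change, and neither document gives a rule for drawing a subgroup conclusion. All of that is correct. A reader might infer that the SAP judges the subgroup by these tests; it does not say so. The risk lies in how the p-values will be read when no contrast stands beside them.

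Four further inferences also go beyond the documents.

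- *That discordant results occur about half the time whatever the effect.* This needs a true change near 0.9 with SD 3.562. SAP 3 gives 0.9 as the change the trial is powered to detect and does not call it the expected change. Step 3 shows how quickly the figure falls at larger changes.
- *That unequal subgroup size is the main cause.* The figure is already 50% at an equal split. Low power within each subgroup drives it, and imbalance makes it worse.
- *That separate models are fitted to Yes and No.* With no prior-treatment term in the model this is a natural reading, but the SAP does not state it, and the group in SAP 6.4.1.3 could mean treatment arm within subgroup. The contrast is missing on either reading.
- *That small pooled sites will break the subgroup fits.* SAP 6.4.1.1 allows site to be dropped if it causes modelling problems, and site enters as a main effect only.

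It can also be said that LS means and CIs for each subgroup are already implied, so a reader could form the difference by hand if the fits are separate. That is partly true, but it leaves the key quantity to the reader while p-values against zero are printed. Finally, the contrast has little power. That is a reason to present it as an estimate with a CI; it does not justify leaving it out.

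**Conclusion.** The point holds in a limited form. The only planned subgroup analysis compares each group's change with zero and does not estimate whether the change differs by prior OAB treatment. This follows from the wording of both documents and needs no assumed effect or split.

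The size of the risk does rest on assumptions: equal true changes, a one-sample t-test in place of the MMRM, SD 3.562 and an assumed split. At the planning values a discordant pair of results is as likely as not or somewhat more likely; at changes of about 1.8 or above it is much less likely. Baseline adjustment could lower the SD, while fitting site in small subgroups could cost precision, so the MMRM figures may differ in either direction.

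The primary conclusion and the estimand are not touched. The change is worth making because it is cheap and because the present output invites a misreading.

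**What to change.** In SAP 6.4.1.3, fit one MMRM on the whole FAS, adding prior OAB treatment and its interactions with treatment, visit and treatment-by-visit to the SAP 6.4.1.1 model. Report:

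- the Week 12 LS mean change on 50 mg in each subgroup, with 95% CI;
- the Yes-minus-No difference within the 50 mg arm at Week 12, with 95% CI. If a p-value is given, state that it belongs to this contrast and not to the interaction of prior treatment with 25 versus 50 mg, which is a different question.

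Label the result exploratory, note that prior treatment is not randomised, and state that within-subgroup p-values against zero will not be used to infer a subgroup difference.

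The cost is SAP wording and one model specification. No new data or patients are needed. The downside is the wide interval, and a non-significant contrast must not be read as evidence of no difference.

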### 6.4.2 Analysis of Secondary Efficacy Endpoints

### 6.4.2.1 Analysis of Secondary Efficacy Endpoints at Week 12

The same primary efficacy analysis (MMRM, with corresponding baseline measurement for the endpoint as the covariate) as for the primary endpoint (except for the covariate, i.e., mean number of micturitions at baseline) will be applied to change from baseline at the end of the 12-week treatment period in Mirabegron 50 mg subjects for:

- Mean number of grade 3 or 4 (PPIUS) urgency episodes per 24 hours
- Mean number of daytime incontinence episodes per 24 hours
- Mean number of nighttime incontinence episodes per 24 hours

- Mean number of urge incontinence episodes per 24 hours
- OAB Symptom Score

For each of the endpoints above, the covariate included in the model will be the respective variable of interest at the baseline, e.g., OAB Symptom Score at baseline for change from baseline to week 12 for the OABSS endpoint.

Data of these secondary efficacy endpoints will be analyzed for the FAS.

#### 6.4.2.2 Analysis of Secondary Efficacy Endpoints at Weeks 4 and 8

For each treatment group, separately, least squares (LS) means ( $\pm$  standard error [SE]) along with 2-sided 95% Cis, from the same analysis model described in Section 6.4.2.1, will be presented for changes from baseline at Weeks 4 and 8.

#### 6.4.2.3 Analysis of Secondary Efficacy Endpoints for Mirabegron 25 mg Starting Dose

Secondary efficacy endpoints presented in Section 5.2.6 will be summarized for Mirabegron 25 mg starting dose by visit (week 0, 4, 8 and 12) following the same statistical methods described in Sections 6.4.2.1 - 6.4.2.2 and will be conducted on the FAS.

#### 6.4.2.4 Graphical Summary of Data from Mean Number of Grade 3 or 4 (PPIUS) Urgency Episodes and Urge Incontinence Episodes per 24 hours

Mean number of grade 3 or 4 (PPIUS) urgency episodes per 24 hours at each visit and mean number of urge incontinence episodes per 24 hours at each visit will be plotted for FAS: mean (SEM) values will be presented for each visit.

### 6.5 Analysis of Safety

Safety analysis will be conducted on the SAF. Safety endpoints will be summarized by treatment group and visit, if applicable. Descriptive statistics will be presented.

All safety summaries (except for shift tables in Sections 6.5.2 and 6.5.4) will be presented by the following:

- Mirabegron 25 mg
  - Never Up-Titrated
  - Later Up-Titrated to 50 mg (at visit 3 or 4)
  - Total
- Mirabegron 50 mg
  - $\circ$  as Randomized
  - Up-Titrated from 25 mg (at visit 3 or 4)
  - Total
- Total Mirabegron, i.e., the sum of the Mirabegron 25 mg (Total) and of Mirabegron 50 mg (As-Randomized)

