### 5.4.1 Adverse Events

AEs will be coded using MedDRA. A TEAE is defined as an AE observed after starting administration of the IP until 30 days after the final administration of IP. If the adverse event occurs on Day 1 and the onset check box on the (AE) eCRF is marked "Onset after first dose of study drug" or the onset check box is left blank, then the adverse event will be considered treatment emergent. If the adverse event occurs on Day 1 and the onset check box is marked "Onset before first dose of study drug", then the adverse event will not be considered treatment emergent. If a subject experiences an event both during the pre-investigational period and during the investigational period, the event will be considered as TEAE only if it has worsened in severity (i.e., it is reported with a new start date).

A drug-related TEAE is defined as any TEAE with at least possible relationship to study treatment as assessed by the investigator or with missing assessment of the causal relationship.

AEs may be upgraded by the sponsor according to the Important Medical Event process.

A drug-related TEAE is defined as any TEAE with at least a possible relationship to study treatment as assessed by the investigator or with a missing assessment of the causal relationship.

Common TEAEs are defined as preferred terms (PTs) that have been reported by at least 5% of the subjects, in any treatment group.

When an AE start or stop date is missing, the date will be imputed using the rules in Section 6.10.2.2.

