Additionally, for groups with both a baseline and week 12 measurement (i.e., Mirabegron 25 mg [Never Up-Titrated], Mirabegron 50 mg [As-Randomized] and Total Mirabegron) a within-subject change will be calculated as the post-baseline measurement minus the baseline measurement and summarized in the same way. Each laboratory result will be classified as low (L), normal (N), or high (H) at each visit according to the laboratory supplied reference ranges.

The number and percentage of subjects below and above reference range will be summarized by treatment group and visit.

Frequency tabulations of qualitative clinical laboratory variables (urinalysis) will be presented by treatment group and visit.

Summary shifts of reference range (low, normal, high) changes from baseline to week 12 will be presented by the following treatment groups:

- Mirabegron 25 mg (Total)
- Mirabegron 50 mg (As-Randomized)
- Total Mirabegron, i.e., the sum of the Mirabegron 25 mg (Total) and of Mirabegron 50 mg (As-Randomized).

These shifts are categorized as:

- "Shift to Low": shift from normal or high to low
- "Shift to High": shift from normal or low to high
- "Categorized Increase": shift from low to normal or from normal to high
- "Categorized No Change": value stays in the same reference range
- "Categorized Decrease": shift from high to normal or from normal to low.

All clinical laboratory data collected during the study and variables derived from it will be listed using SAF.

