#### 6.10.2 Imputation Rules for Incomplete Dates

As a general principle, no imputation of missing data for variables will be done. Exceptions are the start and stop dates of AEs and concomitant medication. The imputed dates will be used to allocate the concomitant medication and AEs to a treatment group, in addition to

determining whether an AE is/is not treatment emergent. Listings of the AEs and concomitant medications will present the actual partial dates; imputed dates will not be shown.

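### In the safety tables, Total Mirabegron is defined by a sum that, read with the implied split at dose escalation, omits post-escalation events while keeping the subjects in the denominator

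*SAP*

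**What the plan says.** SAP 6.5 sets the columns for all safety summaries except the shift tables of 6.5.2 and 6.5.4. Under 25 mg they are Never Up-Titrated, "Later Up-Titrated to 50 mg (at visit 3 or 4") and Total. Under 50 mg they are as Randomized, "Up-Titrated from 25 mg (at visit 3 or 4") and Total. A last column is defined as "Total Mirabegron, i.e., the sum of the Mirabegron 25 mg (Total) and of Mirabegron 50 mg (As-Randomized").

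Other SAP sections bear on what these cells hold:

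- 5.4.1: "A TEAE is defined as an AE observed after starting administration of the IP until 30 days after the final administration of IP". An event after escalation is therefore treatment-emergent.
- 4.4: the safety set is everyone who took at least one dose.
- 6.10.2: "The imputed dates will be used to allocate the concomitant medication and AEs to a treatment group".
- 6.5.2: within-subject laboratory change is calculated "for groups with both a baseline and week 12 measurement (i.e., Mirabegron 25 mg [Never Up-Titrated], Mirabegron 50 mg [As-Randomized] and Total Mirabegron").
- 6.4.1.1, on subjects who switch: "Data from those subjects prior to switching will still be included in the MMRM model with treatment equal to 25 mg".
- 5.5.1 and 6.3: exposure is divided by dose.

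SAP 6.2 uses the same sum for study population summaries.

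**The concern.** An escalated subject has one cell under 25 mg and another under 50 mg. If the first holds data up to the switch and the second holds data after it, the Total Mirabegron sum takes in the first and leaves out the second. The subject enters N through 25 mg (Total), but an event that begins after escalation enters no term of the numerator.

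For adverse event percentages the error runs one way: overall incidence comes out too low, and the missing events are those that follow a dose increase. The study is meant to support licence renewal and safety surveillance (SAP 2.2). No other column can stand in. Each of the others covers part of the subjects or part of their time, and adding 25 mg Total to 50 mg Total counts escalated subjects twice.

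In SAP 6.2 the same sum does no harm, because population summaries count each subject once and are not divided by dose.

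**Working it through.** **Step 1. Is the split at the switch supported?** The SAP has no explicit rule, so the evidence has to be set side by side.

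- Layout (6.5): the same people fill Later Up-Titrated under 25 mg and Up-Titrated under 50 mg. Two cells are needed only if their data are divided.
- Dates (6.10.2): imputed dates allocate events to a treatment group, in addition to deciding treatment emergence. A date matters for this only if a subject's group can change over time.
- Laboratory change (6.5.2): the groups named as having both baseline and week 12 omit Later Up-Titrated and 25 mg (Total), which implies that post-switch values are not held under 25 mg.
- Efficacy model (6.4.1.1): switchers contribute to 25 mg [total] only before the switch.
- Exposure (5.5.1, 6.3): days are counted by dose.

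One place points the other way. The laboratory shift tables in 6.5.2 show 25 mg (Total) from baseline to week 12. That group can include an escalated subject's week 12 value only if post-switch data are in it. The ECG shift tables in 6.5.4 use 25 mg (Never Up-Titrated) instead. The label 25 mg (Total) therefore has two meanings.

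**Step 2. The SAP's own exposure example (5.5.1).** First dose 1 July, escalation 29 July, last dose before interruption 1 August, restart 5 August, last dose 23 September 2020.

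- Total: 85 − 3 = 82 days.
- At 25 mg: 28 days.
- At 50 mg: 4 + 50 = 54 days.

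All three match the SAP. The exposure tables have no Total Mirabegron column, but the example shows the scale: under the 6.5 sum, this subject's 28 days at 25 mg are inside the overall column and 54 of 82 days (66%) are outside it.

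**Step 3. Scheduled laboratory, ECG and PVR values.** These are taken at screening and week 12/EoT only (Protocol Table 1; SAP 5.4.3, 5.4.5, 5.4.6). Escalation happens at week 4 or 8. Every escalated subject's scheduled post-baseline value is thus taken on 50 mg, and under the split it lies outside the overall column in the non-shift summaries. This needs no assumption about event rates.

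**Step 4. Size for adverse events.** Inputs: 249 randomized (SAP 9.1); about 166 planned on 50 mg (SAP 3), leaving 249 − 166 = 83 on 25 mg; 84 days of treatment; event window 84 + 30 = 114 days. Assumptions: escalated fraction f (not given in the documents), all escalation at one visit, constant hazard, no dropout.

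- Share of treatment time omitted = 83·f·d / (249 × 84), with d = 56 days after week 4 or 28 days after week 8.
- Incidence shown = [(249 − 83f)·p + 83f·(1 − exp(−h·s))] / 249, with h = −ln(1 − p)/114 and s = 28 or 56 days before the switch.

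For p = 0.30, h = 0.3567/114 = 0.00313, and 1 − exp(−hs) is 0.0839 (s = 28) or 0.1607 (s = 56). With f = 0.5 there are 41.5 escalators:

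- Week 4: (207.5 × 0.30 + 41.5 × 0.0839)/249 = 65.7/249 = 26.4%.
- Week 8: (62.25 + 41.5 × 0.1607)/249 = 68.9/249 = 27.7%.
- True: 74.7/249 = 30%. About 6 (week 8) to 9 (week 4) subjects with an event are missed.

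| Escalating | Time omitted, all at week 8 | Time omitted, all at week 4 | True 30% shows as (week 8 / week 4) |
|---|---|---|---|
| 30% | 3.3% | 6.7% | 28.6% / 27.8% |
| 50% | 5.6% | 11.1% | 27.7% / 26.4% |
| 70% | 7.8% | 15.6% | 26.8% / 25.0% |
| 100% | 11.1% | 22.2% | 25.4% / 22.8% |

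**The case against.** The strongest reply is that 25 mg (Total) may mean everyone who started on 25 mg, with all their data. The sum would then count each subject once and lose nothing, and the authors may have chosen it just to avoid double counting. The laboratory shift tables in 6.5.2 fit that reading. This stands as far as it shows that the split is inferred and the label inconsistent. It does not settle the matter, because 6.5 exempts those shift tables from its layout, and under that reading the separate 50 mg Up-Titrated cell would duplicate data already under 25 mg.

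Four stronger readings are tempting and are not supported:

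- That SAP 6.10.2 states a dose-at-onset rule. It covers incomplete dates and speaks of a treatment group; the rule has to be inferred.
- That the events vanish from the report. They remain in the 50 mg Up-Titrated and 50 mg Total columns, and adverse events are listed by subject (6.5.1).
- That every post-escalation event lowers the incidence, or that readings are diluted too. A subject who already had the same event on 25 mg is still counted. The denominator argument applies to event percentages; in by-visit means a missing value lowers n.
- That Total Mirabegron is the study's principal safety result. The SAP does not say so, and Protocol 4.3 gives the 50 mg group the primary efficacy and safety role. The column is descriptive and no test depends on it.

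**Conclusion.** The concern holds as a defect of definition. SAP 6.5 gives a sum for Total Mirabegron that leaves out one cell of its own layout. Under the split that most of the SAP implies, that cell holds the post-escalation treatment-emergent events and the escalators' week 12 laboratory, ECG and PVR values in non-shift summaries. Overall event incidence is then understated, and no column gives incidence across all treated subjects.

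The size depends on an escalation rate that the documents do not give. From 30% to 100% escalation, 3.3% to 22.2% of treatment time is omitted. At 50%, a true 30% incidence shows as 27.7% to 26.4%. These figures rest on 83 and 166 subjects, constant hazard and no dropout, although the plan allows for 25% dropout. The primary efficacy analysis is not affected.

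**What to change.** In SAP 6.5 and the table shells:

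1. Define Total Mirabegron as all safety-set subjects, each counted once in N and at most once per event category, with all data from first dose to 30 days after last dose at either dose.
2. State that in the dose-split columns an adverse event is assigned to the dose being taken at onset.
3. State that in the laboratory shift tables of 6.5.2, 25 mg (Total) means all subjects who started on 25 mg, with their week 12 value at either dose.

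Leave the sum in SAP 6.2 unchanged. With point 1 in place, the example subject of SAP 5.5.1 would contribute 82 of 82 days to the overall column.

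The cost is wording and table shells. No new data are needed, and the reported overall incidence may be slightly less favourable.
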